Memory Enhancement Training (MET): Memory training is based on the notion that cognition is plastic in older age (A. Acevedo & Loewenstein, 2007). Traditional memory training interventions facilitate plasticity by teaching people mnemonic techniques involving verbal association and visual imagery and practical strategies that boost encoding and retrieval (Gross et al., 2012; Verhaeghen, Marcoen, & Goossens, 1992). A meta-analysis of 33 clinical trials including data from over 1,500 older adults showed that gains on objective memory tests following memory training are large (i.e. on average, a standardized mean difference from pretest to posttest of .73) compared to the small-medium sized effects for control (.37) and placebo (.38) conditions. A more recent metaanalysis (Gross et al., 2012) of 35 studies reported that memory training effects remain significant after controlling for practice effect. The overall estimate of effect size (the mean standardized difference in pre-post change between memory-trained and control groups) was 0.31 standard deviations (SD); the pre-post training effect for memory-trained interventions was 0.43 SD and the practice effect for control groups was 0.06 SD. Effective mnemonic memory enhancement methods involved visual imagery, verbal associations, story mnemonics, organizational encoding strategies, and the use of multiple techniques, and no specific strategy is better than another (Bjorklund, Schneider, Cassel, & Ashley, 1994; Gross et al., 2012; Stigsdotter & Bäckman, 1989; Verhaeghen et al., 1992; Willis et al., 2006). Benefits from memory training may last from six months to five years (Verhaeghen et al., 1992; Willis et al., 2006). Memory training can transfer to daily life when participants are given homework practice and training in using techniques in daily life and novel situations (McDaniel & Bugg, 2012). Small group interventions, memory education, and relatively short sessions (e.g. 90 minutes or less) are other important components of training programs (Verhaeghen et al., 1992). Memory training also improves subjective memory functioning but effect sizes are smaller (.30) compared to the effect on objective test performance (Floyd & Scogin, 1997). We chose to implement mnemonic methods over computerized memory training programs because the former have a longer history of implementation in aging populations and have more empirical evidence supporting their use in older adults. The MET program in the current proposal includes evidence-based techniques and approaches to facilitate transfer of new knowledge to participants' everyday lives.

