We propose a randomized controlled design for this pilot 12-week trial of the behavioral intervention MET compared to KK+KY for improving cognitive performance and health in women at high risk of AD. We hope to control for nonspecific factors by using a gold standard active control condition that has demonstrated acceptability in this population.

The proposed study will to test whether KK+KY is superior to MET for improving cognitive functioning, health (including cardiovascular factors), and mood in women with high AD risk. All participants will be recruited from the UCLA Women's Cardiovascular Center, UCLA outpatient clinics and the UCLA Longevity Center Program. All participants will be identified as having high AD risk including subjective memory complaints and high cardiovascular risk based on the 2013 ACC/AHA Guideline on the Assessment of Cardiovascular Risk (Goff et al., 2014). Follow up of all enrolled subjects at 6- and 12-months (52 weeks total) will allow detection of any continued cognitive or health benefits.

b) Methods for reducing risk of bias:

Participants will be informed prior to enrollment that they will receive one of two evidence-based interventions for improving memory. Descriptions of the study will be designed to minimize risk of possible between group differences resulting from differences in treatment expectancy. Differences in treatment expectancy/ credibility will be tested for at baseline, week 12, and week 24 as specified below. We will also control for the "instructor" effect if several instructors teach classes. The feasibility of weekly yoga/MET classes and homework time was assessed during previous studies and found reasonable for participants to complete (Eyre et al., 2016; H. Yang et al., 2016). Behavioral raters will be blind to group assignment.

1. Study Population: We anticipate screening about 250 subjects to recruit 100 women with subjective memory complaints and high cardiovascular risk based on the 2013 ACC/AHA Guideline on the Assessment of Cardiovascular Risk. Participants will be recruited from the women's clinics and geriatric clinics at UCLA as well as the UCLA Longevity Center.

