Power analysis: The power analysis is focused on the primary aim of the study to assess whether the KK+KY and MET groups demonstrate comparable improvement in memory performance. We plan to enroll a total of 100 women in the study, anticipating an attrition rate of at most 10% based on our previous studies. Thus, we will most likely have a total of 90 completers. With a sample size of 45 per group, we achieve 80% power to detect equivalence within a margin of equivalence of 0.62, when the true difference between the means is assumed to be zero. In the PI's previous study using similar interventions on older adults with MCI, a between-group effect size of 0.3-0.4 was observed for the memory measures. In the proposed study, the target population is women with high risk for AD, hence we believe that the proposed sample size will have sufficient power to address the primary hypothesis of the study. With this sample size, we can also expect to detect an effect size of 0.60 at a significance level of 0.05 and 80% power for the secondary outcome measure (executive functioning). We intend to test the secondary outcomes adjusting for multiple comparisons using the Benjamini-Hochberg false discovery rate approach (which is more powerful than the simple Bonferroni correction). Further, we will report results of all proposed analyses and conclusions will be based on the pattern of results.

Data management: Data management and analysis support will be provided by the UCLA Semel Institute Statistical Core (SI-Stat) ([name]). The SI-Stat will provide needed software and technical support with a data manager operating under the supervision of [name]. The SI-Stat has a Dell PC computer network with

automated CD R/W backup and is set up for medium to large-scale data processing and analysis using available commercial database and statistical software. **1. Randomization.** Randomization schedules will be prepared in a masked manner by the statistician. **2. Data submission and quality control.** Data forms will be delivered from the originating location to the central data unit within one week of being generated. When errors, omissions, or unclear information is detected on the paper forms, a copy will be returned for corrections. The data manager will generate monthly reports summarizing missing and incorrect data will be sent to the PI.

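### The 0.62 equivalence margin is 1.7 to 2 times the net effect of memory training in the plan's own background, so equivalence at that margin would not show that KK+KY keeps any of MET's benefit

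*Combined protocol and SAP*

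**What the plan says.** The Power analysis section gives the primary aim as "to assess whether the KK+KY and MET groups demonstrate comparable improvement in memory performance". With 45 completers in each arm, its claim is: "we achieve 80% power to detect equivalence within a margin of equivalence of 0.62, when the true difference between the means is assumed to be" (no difference). The margin has no unit and no rationale.

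MET is the only comparator. Study Design (a) says the trial controls for nonspecific factors "by using a gold standard active control condition that has demonstrated acceptability in this population". Randomisation is 1:1 to KK+KY or MET, with no untreated arm.

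The background paragraph on MET cites two meta-analyses. For the more recent one, the overall effect, defined as "the mean standardized difference in pre-post change between memory-trained and control groups) was 0.31 standard deviations (SD"), comes with separate pre-post figures of 0.43 SD for trained groups and 0.06 SD practice gain for controls. The older one reports gains of "a standardized mean difference from pretest to posttest of .73) compared to the small-medium sized effects for control (.37) and placebo (.38) conditions".

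The Data analysis section specifies a linear mixed model with group, time and their interaction, tested two-sided at 0.05. It contains no equivalence test, no margin and no interval level. Hypothesis 1 separately expects memory to improve from baseline to 12 weeks in both arms.

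**The concern.** When the only comparator is an active treatment, showing that two arms are close supports the new one only if the margin is no larger than what the comparator adds over no treatment. Otherwise an arm that has lost the whole of that benefit still falls inside the margin.

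Here the margin exceeds every estimate of memory training's net effect that the plan cites. A result inside ±0.62 would therefore be compatible with KK+KY giving nothing on memory beyond retest practice, yet it could be reported as comparable improvement. The fault lies in the size of the margin. It is not cured by adding a formal equivalence test at 0.62, and better precision makes it more likely that a no-effect arm passes.

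**Working it through.** **Inputs.** From Power analysis: 45 per group, margin 0.62, true difference 0, power 80%. From Data analysis: alpha 0.05. From the MET background: net training effect 0.31 SD directly; 0.43 − 0.06 = 0.37 from the separate figures; 0.73 − 0.38 = 0.35 and 0.73 − 0.37 = 0.36 from the older meta-analysis. Assumed, because not stated: SD = 1, so the margin is in SD units, and two one-sided t-tests at 0.05 each.

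**Reproducing the 80%.** SE = √(2/45) = 0.211. With d the true difference, the normal form is

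P = Φ((0.62 − d)/SE − 1.645) − Φ((−0.62 − d)/SE + 1.645).

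At d = 0: 0.62/0.2108 = 2.941; 2.941 − 1.645 = 1.296; P = 2 × 0.9025 − 1 = 0.805. The exact t-based version (88 df) gives 79.7%. At 0.025 per side it gives 65.7%, which does not match. If 0.62 were in raw units of an average of three z-scores with assumed correlations of 0.3 to 0.7, power would be 98% to 89%, which does not match either. SD units with 0.05 per side is the reading that reproduces the document.

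**Margin against effect.** 0.62/0.31 = 2.0; 0.62/0.37 = 1.7.

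**Chance that a no-effect arm is declared equivalent (exact t).** If KK+KY yields only practice gain, d equals MET's net advantage.

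| MET's net advantage (SD) | Declared equivalent |
|---|---|
| 0.31 | 42% |
| 0.35 | 35% |
| 0.36 | 34% |
| 0.37 | 32% |
| 0.53 | 11% |

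Normal-form check at 0.31: Φ(−0.174) − Φ(−2.767) = 0.431 − 0.003 = 0.428.

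The last row is an assumption built from Table 2. MET's 12-week gains over baseline SD are 2.88/5.42 = 0.53, 1.00/2.26 = 0.44, 5.73/7.90 = 0.73, 1.00/2.39 = 0.42 and 4.42/5.29 = 0.84, averaging 0.59; less 0.06 practice, 0.53.

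With baseline adjustment at an assumed r = 0.5 to 0.7 (residual SD √(1 − r²)), the 42% rises to 52% to 65%.

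**Adding Hypothesis 1.** Simulated: equivalence at 0.62 and a significant gain in KK+KY (paired t, two-sided 0.05), with 45 per group. Change-score SD = √(2(1 − r)), which is 1 at r = 0.5 and 0.77 at r = 0.7 (assumed).

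| Practice gain (KK+KY) | MET gain | Both conditions met, SD 1 | Both conditions met, SD 0.77 |
|---|---|---|---|
| 0.06 | 0.37 (0.06 + 0.31) | 5% | 7% |
| 0.37 | 0.73 | 32% | 47% |

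**Power at a 0.31 margin.** The 90% interval half-width is 1.662 × 0.2108 = 0.350, already wider than 0.31. Power at d = 0 is 0.3% unadjusted, and 6%, 15% and 31% with baseline adjustment at assumed r = 0.5, 0.6 and 0.7.

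**The case against.** A reader might infer that the plan will declare an ineffective yoga programme equivalent 42% of the time. The documents do not support that as it stands. The analysis sections contain no equivalence rule, so the percentage describes a test implied by the power statement. It also moves with MET's true advantage, from 42% down to about 11% across the values above. No single figure should carry the point.

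A reader might also infer that nothing else in the plan could expose a no-effect arm. Hypothesis 1 requires KK+KY to improve on its own baseline, and most of the tests have alternate forms for repeat testing. If practice gain is 0.06 SD, the joint condition is met only 5% to 7% of the time. That part of the objection stands. It fails if practice is nearer the 0.37 SD that the older meta-analysis reports for controls.

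A third tempting reading is that passing at 0.62 leaves KK+KY plausibly about 0.3 SD worse than no training. That is the extreme edge: a true deficit of 0.62 passes only 5% of the time, and at SD 1 passing needs an observed difference below about 0.62 − 0.35 = 0.27.

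Finally, the plan calls itself a pilot and says it will judge on the pattern of results. This lowers the severity. It does not limit what may be claimed from that pattern, and the same section says the sample is sufficient for the primary hypothesis.

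**Conclusion.** The concern holds in a bounded form. The margin is 1.7 to 2 times the net effect of memory training in the plan's own background and is not justified. With no untreated arm, equivalence within 0.62 cannot show that KK+KY retains any of MET's benefit. Under the implied test, a no-effect arm passes 32% to 42% of the time for a MET advantage of 0.37 down to 0.31 SD.

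This rests on SD units, one-sided 5% tests, and MET performing here as in the cited literature. The margin-to-effect comparison needs only the first and last of these. MET's effect in this population is unknown, and on the Table 2 reading (0.53) the margin still exceeds it.

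A reader might conclude that the trial should be re-powered at 0.31. At 45 per group that is not workable. The point is a worthwhile, inexpensive correction to interpretation, not a defect that must be cured before the trial can proceed.

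**What to change.** Keep the sample size and amend the Primary outcome and Power analysis text:

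1. Report the week-12 KK+KY minus MET difference in the memory composite with its confidence interval, the level fixed in advance, read against both 0.31 and 0.62 in stated units.
2. Say that the 80% applies only to showing that the arms differ by less than 0.62 SD, and that the trial is not powered to show retention of MET's benefit (0.3% at a 0.31 margin unadjusted; about 6% to 31% with baseline adjustment at assumed r = 0.5 to 0.7).
3. Say that an interval inside ±0.62 but crossing −0.31 does not show that KK+KY improves memory or matches MET, and that gain from baseline within an arm does not settle this because it includes practice.

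This needs no extra participants or visits. The price is that the stated 80% no longer supports an effectiveness claim on memory, and the primary result becomes an estimate with an interval.

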Data will be analyzed using the SAS (v9.4) statistical package. Data will be examined initially to identify issues such as departures from normality, which might suggest the need for transformation (e.g., logarithmic). Demographic variables (e.g., age, gender, etc.) will be compared by treatment group and examined in relation to outcome variables; this would define one possible set of appropriate covariates, if needed. Correlations (a) among outcome measures and (b) among potential covariates will be examined to eliminate redundancy via possible data reduction, e.g., formation of composite scores or selection of single measures from sets of highly inter-correlated variables. Cognitive domain scores will be obtained as follows: for each neuropsychological test, raw scores will be converted to standardized (Z) scores with a mean of 0 and a SD of 1, based on all participants combined. Then, for each of the tests in a cognitive domain, the Z scores will be averaged to create a single Z score per cognitive domain.

The independent samples *t*-test or Chi-square test will be used to compare the demographic characteristics between the MET and KK+KY control group. The effect of intervention over time on the cognitive functions will be investigated in intention-to-treat (ITT) analyses. Measurements will be analyzed using linear mixed models; analyses will assume missing at random with missingness allowed. All models will include random intercepts to account for correlations between the repeated measures for each participant. The fixed components of the models will include effects of group and time and a group X time interaction, with post hoc analyses between times and groups. All statistical significance tests will be two-sided, and an alpha-level of 0.05 will be considered statistically significant for primary analyses and Bonferroni correction will be employed for post hoc analyses.

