Primary outcome: The analyses for the memory domain Z scores will use general linear mixed model (GLMM) analysis (e.g., SAS PROC MIXED). The two treatment groups will be compared for time course of cognitive domain z scores the initial endpoint EOT at 12 weeks and 6- and 12-months. Covariates may be included in the model as noted above. As noted above, the primary cognitive domain of interest for this proposal is memory. A separate GLMM as above will be estimated using memory domain z-scores as dependent variables. Executive Function will be examined as secondary outcome measure. Supplementary analyses of the follow-up period will look at the cognitive domain scores by treatment group controlling for values at EOT (post-treatment changes). Objective memory measures will be examined using a similar GLMM.

Exploratory Hypotheses: GLMM models as described above will be used to examine telomerase activity (overall level and TL) and inflammatory measures separately. Relationships between changes in markers of inflammation and telomerase activity to changes in cognitive scores, cognitive domain scores and fMRI measures will be examined using regression models within each group. Transformations of the measures will be performed as necessary.

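### The trial is sized for equivalence in memory within 0.62, but the analysis section has no equivalence rule, and power is called sufficient without a figure at any non-zero difference

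*Combined protocol and SAP*

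**What the plan says.** **Power analysis.** The stated aim is to see whether the two groups "demonstrate comparable improvement in memory performance". With 100 enrolled and at most 10% attrition, the plan counts on 45 per group and claims "80% power to detect equivalence within a margin of equivalence of 0.62, when the true difference between the means is assumed to be zero". It then reports that in the previous study, in adults with MCI, "a between-group effect size of 0.3-0.4 was observed for the memory measures". It notes that the present population is different and concludes: "hence we believe that the proposed sample size will have sufficient power to address the primary hypothesis of the study". It gives no expected difference for this population, no power at a non-zero difference, and neither units nor a rationale for 0.62.

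**Data analysis.** The model is a linear mixed model with random intercepts: "The fixed components of the models will include effects of group and time and a group X time interaction". On testing: "All statistical significance tests will be two-sided, and an alpha-level of 0.05 will be considered statistically significant for primary analyses". The Primary outcome paragraph adds: "The two treatment groups will be compared for time course of cognitive domain z scores". No margin, pair of one-sided tests or confidence-interval criterion appears.

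**Elsewhere.** Hypothesis 1 under Specific Aims is improvement from baseline within each arm at 12 weeks. Study Design, part (a), says the study tests superiority of KK+KY over MET on cognitive functioning. The Background on MET cites a meta-analysis in which "the mean standardized difference in pre-post change between memory-trained and control groups) was 0.31 standard deviations (SD"), with pre-post gains of 0.43 SD (trained) and 0.06 SD (practice in controls). It also cites an older meta-analysis with .73 against .37. Measures and Outcomes says that all outcomes are collected at week 12. Its paragraph on neuropsychological tests lists only baseline, 6 and 12 months, and Table 4 has no week-12 mark for the battery.

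**The concern.** An equivalence sample size means something only if the analysis applies the matching rule. Here the sample size rests on one test and the analysis section specifies another. Failing to reject a two-sided group-by-time test does not show that two arms are comparable; with 45 per group it may show only that the trial is small.

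The sufficiency claim has a second gap. In a superiority trial a prior effect of 0.3-0.4 would be the effect to detect. In an equivalence trial a non-zero true difference lowers power, so the cited effect works against the claim it is placed beside. Finally, a margin wider than the benefit of training over control cannot alone support the statement that yoga matches the benefit of memory training.

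**Working it through.** **Inputs.** From Power analysis: n = 45 per group, margin 0.62, true difference 0, prior effect 0.3-0.4. Assumed because not stated: outcome SD 1 (so 0.62 is in SD units), 5% per one-sided test, and every correlation below.

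**1. The plan's own figure.** Equivalence is declared if |D| + t(0.95; 88) × s × √(2/45) < 0.62, where √(2/45) = 0.2108. Normal approximation to power at true difference d:

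Φ((0.62 − d)/0.2108 − 1.645) + Φ((0.62 + d)/0.2108 − 1.645) − 1.

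At d = 0 this is 2Φ(1.296) − 1 = 80.5%; the exact t version gives 79.7%. At 2.5% per side it is 65.7%. So the stated 80% needs 5% per side, that is, a 90% CI.

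**2. Units.** The outcome is an average of z-scores from three tests. With inter-test correlation r, its SD is √((1 + 2r)/3), which is 0.73 at r = 0.3 and 0.89 at r = 0.7. If 0.62 were in averaged-z units, it would be 0.69-0.85 composite SD, with 89-98% power at zero. The stated 80% therefore fits SD units of the composite.

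**3. Power away from zero.** The planned group-by-time contrast is close to a difference in change, with SD √(2(1 − ρ)) for baseline correlation ρ. Exact power:

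| Basis | d = 0 | d = 0.3 | d = 0.4 |
|---|---|---|---|
| Unadjusted, or change at ρ = 0.5 | 80% | 44% | 27% |
| Change, ρ = 0.6 | 89% | 51% | 31% |
| Change, ρ = 0.7 | 97% | 62% | 38% |
| Change, ρ = 0.8 | >99% | 77% | 50% |

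**4. What the pilot table implies for change.** From Table 2 (MET minus KY at 12 weeks), differences in means are 0.23-0.36 pooled SD. Differences in change, in baseline SD, are: HVLT total 0.26, HVLT delayed 0.22, WMS immediate 0.07, WMS delayed −0.19, Rey-O 3-min 0.27, Rey-O 30-min 0.31.
- Three delayed scores (Table 3): (0.22 − 0.19 + 0.27)/3 = 0.10.
- Three tests as in the primary-outcome definition: HVLT (0.26 + 0.22)/2 = 0.24; WMS (0.07 − 0.19)/2 = −0.06; Rey-O 0.27; mean 0.15.
- In composite SD: 0.10/0.89 = 0.11 up to 0.15/0.73 = 0.21.

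Power across 0.11-0.21 is 74-60% at ρ = 0.5, 92-80% at ρ = 0.7 and 98-92% at ρ = 0.8.

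**5. What the planned test would miss.** For a true difference of 0.31 SD, an unadjusted two-sided 5% t-test with 45 per group has about 31% power, so it misses the difference about 69% of the time. On the change scale, 0.31/(0.775 × 0.2108) = 1.90 standard errors at ρ = 0.7 (missed about 53%) and 0.31/(0.632 × 0.2108) = 2.33 at ρ = 0.8 (missed about 37%).

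**6. The margin against the cited training effect.** Training over control is 0.31 SD directly, 0.43 − 0.06 = 0.37 or .73 − .37 = .36 by subtraction. On a common scale, 0.62/0.37 = 1.7 and 0.62/0.31 = 2.0. If the cited effects are in per-test SDs, multiplying by 0.73-0.89 gives ratios from 0.73 × 1.68 = 1.2 to 0.89 × 2.0 = 1.8. The margin is larger in every case.

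**The case against.** The zero-difference condition is disclosed, the 80% is correct, and quoting equivalence power at zero is an accepted convention. All of that stands.

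A reader might infer that the real power is 44% or 27% and that the trial is too small. The documents do not support this. The 0.3-0.4 comes from an MCI population and is not offered as the expected difference. It lies near the pilot's differences in 12-week means, whereas the planned contrast is a difference in change, for which the pilot suggests 0.11-0.21. The figures also depend on scale: a per-test 0.3-0.4 would be 0.34-0.55 composite SD.

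A reader might also infer that the margin is simply twice the training effect. That assumes a common scale and applies meta-analytic figures to this MET programme.

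The primary hypothesis said to be adequately powered may be Hypothesis 1, within-arm improvement. With n = 45 and a gain of 0.43 SD, that has 81%, 95% and 99% power at ρ = 0.5, 0.7 and 0.8. So the sufficiency claim may be sound for that question. But the paragraph ties its calculation to comparability, and Study Design names superiority, so the primary question itself needs settling. The protocol calls this a pilot, which argues for leaving the sample size alone, not for leaving out the decision rule.

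**Conclusion.** The concern holds as a mismatch between the powered test and the planned test. This rests on the text alone: the sample size is for equivalence within 0.62 at 5% per side, and the analysis section has no rule by which equivalence could be declared. The sufficiency claim is unsupported as written, because no power is given at a non-zero difference and no difference is expected for this population. Whether 80% holds is undetermined: about 60-98% at the pilot's differences in change and 27-77% at 0.3-0.4, over assumed correlations of 0.5-0.8. The documents give no correlation. The margin is unexplained and exceeds the cited training effect by a factor of about 1.2 to 2.0, depending on scale. This should be fixed, but it does not show that 100 participants are too few.

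**What to change.** Keep 100 participants.

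(a) Reconcile the primary question across Specific Aims (within-arm improvement), Study Design (superiority) and Power analysis (comparability). If equivalence is kept, add to Data analysis that it is declared only if the 90% CI (5% per side) for the 12-week between-group difference in change in the memory composite lies within ±0.62 composite SD. Mark this as an exception to the two-sided rule, and state that a non-significant group-by-time test is not evidence of comparability.

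(b) In Power analysis, state that the 80% is conditional on a zero difference, add power at non-zero differences on the change scale with the assumed correlation labelled, and limit the sufficiency claim to those conditions.

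(c) Justify 0.62, or say that it exceeds the training effect cited in the Background, so that meeting it does not alone show that KK+KY matches the benefit of training.

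(d) Reconcile Measures and Outcomes with Table 4 on whether the memory battery is given at week 12; the rule in (a) needs that score.

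Cost: new wording and no extra participants. If the battery is not now given at week 12, the memory tests would take about 30 + 30 + 5 = 65 minutes each by Table 3. The downside is a less favourable stated power and a possibly inconclusive result.
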